## 1 LIST OF ABBREVIATIONS

6MWD	6 Minute Walk Distance
AE	Adverse Event
BMI	Body Mass index
BP	Blood Pressure
BUN	Blood Urea Nitrogen
CBC	Complete Blood Count
CLIA	Clinical Laboratory Improvement Amendments
CMP	Comprehensive Metabolic Panel
COPD	Chronic Obstructive Pulmonary Disease
CrCl	Creatinine Clearance
CRF	Case Report Forms
CPC	Cancer Protocol Committee
CPET	Cardiopulmonary Exercise Testing
CSA	Cross-Sectional Area
CT	Computerized Tomography
CTCAE	Common Terminology Criteria for Adverse Events
CTQA	Duke Clinical Trials Quality Assurance
DBP	Diastolic Blood Pressure
DCI	Duke Cancer Institute
DE	Dimensional Echocardiography
DSMB	Data Safety Monitoring Board
DUHS	Duke University Health System
FACIT-F	Functional Assessment of Chronic Illness Therapy – Fatigue
FDA	Federal Drug Administration
FKSI-19	Functional Assessment of Cancer Therapy-Kidney Symptom Index -19
GCP	Good Clinical Practice
GLS	Global Longitudinal Strain
HADS	Hospital Anxiety and Depression Scale
HIF $\alpha$	Hypoxia-Inducible Factor alpha
HRQL	Health-related Quality of Life
ICH	International Conference on Harmonization
IFN $\alpha$	Interferon alpha
IMDC	International Metastatic Database Consortium
IRB	Institutional Review Board
ITT	Intent to treat
KPS	Karnofsky Performance Status
LDH	Lactate Dehydrogenase
LVCF	Last Value Carried Forward
LVEF	Left ventricular ejection fraction
mOS	Median Overall Survival
mPFS	Median Progression Free Survival
mRCC	Metastatic Renal Cell Carcinoma
MSKCC	Memorial Sloan Kettering Cancer Center
mTOR	Mammalian Target Of Rapamycin
NCCN	National Comprehensive Cancer Network
NYHA	New York Heart Association
OS	Overall Survival
PDGFR	Platelet-derived Growth Factor Receptor

PI	Principal Investigator
QOL	Quality Of Life
RCC	Renal Cell Carcinoma
RTKs	Receptor Tyrosine Kinases
SBP	Systolic Blood Pressure
SI	International System of Units
SOC	Safety Oversight Committee
SOP	Standard Operating Procedures
TFT	Thyroid Function Test
TKI	Tyrosine Kinase Inhibitor
TUP	Timed Get Up and Go
ULN	Upper Limit of Normal
UPC	Urine Protein Creatinine Ratio
U.S.	United States
VEGF	Vascular Endothelial Growth Factor
VO 2 peak	Peak Oxygen Uptake

## 2 STUDY SCHEMA

[figure not shown]
**Objective:** To investigate changes in cardiopulmonary function in patients treated with sunitinib for metastatic renal cell carcinoma (RCC) on schedule 4/2 and schedule 2/1.

**Design:** Patients with histologically confirmed, treatment-naive metastatic RCC (mRCC), good or intermediate Heng Risk, and Karnofsky Performance Status (KPS)  $\geq 80$  will be enrolled. To be eligible, patients must also have no contraindications to maximal exercise testing and must complete satisfactory exercise testing at baseline.

- Cardiopulmonary exercise testing (CPET) will be performed at baseline, as well as during sunitinib treatment, in order to document changes in peak oxygen consumption ( $VO_2\text{peak}$ ) on each arm.
- Primary determinants of  $VO_2\text{peak}$ , dose intensity of sunitinib, treatment-emergent adverse events (AE), and patient-reported outcomes will also be assessed at similar time points.

Subjects will be randomly allocated to sunitinib treatment at 50 mg daily on one of the two following arms:

- A. Schedule 4/2 (n=15) or
- B. Schedule 2/1 (n=15)

### 3 BACKGROUND AND SIGNIFICANCE

#### 3.1 Renal Cell Carcinoma: Background and Standard Treatments

Renal cell carcinoma accounts for ~3% of all cancers in the United States. This translates to 63,000 new cases a year with 14,000 associated deaths. Metastatic disease is found in 30% of subjects at diagnosis. Close to 90-95% of metastatic disease is of the clear-cell histology. Multiple scoring systems are available to characterize prognosis in treatment-naïve RCC. Two of the most commonly used scoring systems are the Memorial Sloan-Kettering Cancer Center (MSKCC) and the International Metastatic RCC Database Consortium (IMDC). Each of these systems categorizes patients as favorable, intermediate, or poor risk based on how many adverse prognostic factors are present (0: favorable risk; 1-2: intermediate risk; 3 or more: poor risk).

The five parameters included in the MSKCC prognostic score are KPS, nephrectomy status, hemoglobin value, LDH, and corrected calcium concentration. Time from diagnosis to treatment is often used in place of nephrectomy status. The six parameters of importance for IMDC prognostic score classification are Karnofsky Performance Status (KPS), time from diagnosis to treatment, hemoglobin value, corrected calcium concentration, absolute neutrophil count, and platelet count. With each system, total number of adverse prognostic factors present has been shown to correlate with overall survival. Approximately 25% of patients are in the favorable-risk group, 50% are in the intermediate-risk group, and 25% are in the poor-risk group. In an analysis of 1028 patients scored using the IMDC system, median OS for favorable-, intermediate-, and poor-risk patients is 43.2 months, 22.5 months, and 7.8 months, respectively.

Until recently, the cytokines IL-2 and IFN- $\alpha$  were the only active treatments for advanced or metastatic RCC. However, due to each of these agents' limited clinical benefit and substantial toxicity profile, newer targeted agents have largely replaced cytokines in the treatment of advanced or mRCC. The recognition of the importance of hypoxia-inducible factor alpha (HIF $\alpha$ ) signaling in the pathogenesis of clear-cell RCC has led to widespread study of two classes of targeted therapies: anti-angiogenic agents and mTOR inhibitors. Targeting of angiogenesis is rational because constitutive HIF $\alpha$  activation leads to the upregulation or activation of several proteins including vascular endothelial growth factor (VEGF), which can subsequently lead to tumor proliferation and neovasculature formation. Targeting of the mTOR pathway is important because activation of the upstream PI3K/Akt/mTOR signaling pathway is one method by which constitutive HIF $\alpha$  activation or upregulation occurs.

There are 8 targeted agents approved for the treatment of RCC in the United States: 5 that target angiogenesis (i.e., the VEGF-receptor tyrosine kinase inhibitors sorafenib, sunitinib, pazopanib, axitinib, and the VEGF-binding monoclonal antibody bevacizumab), 2 that target the mTOR pathway (i.e., everolimus and temsirolimus), and 1 that targets an immune checkpoint (i.e., the PD-1 inhibitor nivolumab). Among these approved agents, none have demonstrated a statistically significant improvement in overall survival (OS) except for temsirolimus poor-risk patients and nivolumab in VEGF-refractory patients. According to National Comprehensive Cancer Center Network (NCCN) guidelines, sunitinib, temsirolimus (poor risk only), bevacizumab plus interferon, and pazopanib are Category 1 recommendations for first-line therapy of mRCC.

#### 3.2 Study Agent – Sunitinib in Renal Cell Carcinoma

Sunitinib is a VEGF receptor TKI that is approved and recommended for the treatment of mRCC across prognostic groups. In a randomized Phase 3 trial of sunitinib vs. IFN $\alpha$  in treatment-naïve subjects, median progression free survival (mPFS) and median OS (mOS) were greater in the sunitinib group than in the IFN $\alpha$  group (mPFS: 11 mo vs. 5 mo, HR = 0.539; p = < .001; mOS: 26.4 mo vs. 21.8 mo, HR = 0.821; p = .051). The overall response rate (ORR) was also greater in the sunitinib group (47%) than in the IFN $\alpha$  group (12%). More recently, sunitinib was compared to pazopanib in treatment-naïve subjects in the Phase 3 COMPARZ study. In this non-inferiority study, sunitinib and pazopanib demonstrated similar mPFS (8.4 mo for pazopanib vs. 9.5

mo for sunitinib, HR = 1.05) and mOS (28.4 mo for pazopanib vs. 29.3 mo for sunitinib, HR = 0.91; p = 0.28). The ORR of pazopanib and sunitinib was 31% and 24%, respectively. The most common ( $\geq 20$ ) adverse reactions include fatigue, generalized muscle weakness, fever, diarrhea, nausea, mucositis/stomatitis, vomiting, dyspepsia, abdominal pain, constipation, hypertension, peripheral edema, rash, hand-foot syndrome, skin discoloration, dry skin, hair color changes, altered taste, headache, back pain, arthralgia, extremity pain, cough, dyspnea, anorexia, and bleeding [Sunitinib (Sutent®) U.S. Prescribing Information, April 2015]. Other important adverse reactions include hepatotoxicity, QT prolongation (including Torsades de Pointes), osteonecrosis of the jaw, tumor lysis syndrome, and thyroid dysfunction.

### 3.3 Study Purpose/Rationale

#### *Schedule 2/1: An Important Alternative Dosing Regimen of Sunitinib*

A key challenge with sunitinib therapy for mRCC is to maximize quality of life (QOL) by minimizing toxicity without compromising efficacy. Specifically, maintenance of sunitinib dose intensity is related to improved clinical outcomes. A recent Phase III trial provides an example of these difficulties: fatigue was one of the most common treatment-emergent adverse events (AEs), with 63% of sunitinib-treated patients experiencing fatigue, including 17% with grade 3/4 fatigue. Interestingly, 49% of sunitinib-treated patients required dose interruptions of  $\geq 7$  days, and 51% required dose reductions; 20% discontinued treatment due to AEs. More work is clearly needed to achieve this delicate balance.

Preliminary evidence suggests that the alternative schedule 2/1 of sunitinib may maximize both efficacy and tolerability. In theory, schedule 2/1 (2-weeks on, 1-week off) results in more frequent dose interruptions than the standard schedule 4/2 (4-weeks on, 2-weeks off) without affecting dose intensity over the same six-week period. In practice, however, schedule 2/1 may achieve better dose intensity. Multiple retrospective studies comprising over 700 patients have suggested that switching from the standard 4/2 schedule to the alternative 2/1 schedule is associated with both improved outcomes and toxicity profile. Four sets of observations may explain these findings.

- First, maximizing the dose intensity of sunitinib is associated with improved clinical outcomes (PFS and OS).
- Second, both steady state of sunitinib and optimal inhibition of vascular perfusion are reached after 2 weeks.
- Third, an increased compensatory angiogenic response (proliferation of endothelial cells) has been associated with increased time off of sunitinib therapy.
- Fourth, AEs such as fatigue were typically the impetus for dose/schedule modification from schedule 4/2 in the retrospective studies. AEs improved with modification, potentially resulting in fewer dose interruptions and discontinuations due to toxicity.

For example, Atkinson et al demonstrated that the most common AE associated with schedule modification was fatigue (64%), which was reduced to 29% upon follow up after schedule modification. In this study alternative schedule sunitinib, comprised mostly of schedule 2/1 (82%), was also associated with at least comparable time on treatment, PFS, and OS. Further prospective evaluation of sunitinib schedule 2/1 is clearly warranted.

To this end, two prospective single-arm studies are ongoing: (1) to evaluate the tolerability of the 2/1 schedule compared with historical controls (NCT02060370), and (2) to study individualized dosing of sunitinib, including dose reduction to the 2/1 schedule in those who experience treatment-emergent toxicity (NCT01499121). While these studies will provide prospective safety and efficacy data on schedule 2/1, neither trial is comparative or quantitates the functional consequences of treatment-emergent AEs.

### ***Clinical Importance of VO2peak***

Cardiorespiratory fitness testing provides a unique way to measure the tolerability and physiological effects of cancer therapy. The gold standard for direct assessment of cardiorespiratory fitness is peak oxygen consumption (VO2peak). As measured by an objective exercise tolerance test (CPET), VO2peak reflects the integrative ability of the cardiopulmonary system to deliver adequate oxygen and substrate to metabolically active skeletal muscles for ATP resynthesis. Measured or estimated VO2peak is a well-established independent predictor of mortality in a broad range of non-cancer populations. In a series of studies, measurement of VO2peak has also been demonstrated to be safe and well-tolerated in a wide range of cancer patients both during and following therapy. Both a diagnosis of cancer and its associated therapeutic management are associated with significant impairments in VO2peak, while low VO2peak is a significant predictor of physical and functional QOL domains, fatigue, and other patient reported outcomes (PROs). For example, for a given age group (i.e., 60 year olds), compared with healthy women with no diagnosis of breast cancer, patients with breast cancer reached a given VO2peak value about 20 to 30 years earlier. This amounts to “physiologic aging” of several decades in the women with cancer. Finally, VO2peak was demonstrated to be a significant predictor of *overall mortality* in cancer patients, providing prognostic information beyond established factors including performance status. In summary, VO2peak may be an important quantitative marker of change in function due to cancer therapy and is associated with survival in patients with cancer.

### ***Summary: Rationale & Hypothesis***

While 4/2 is the recommended starting sunitinib dosing schedule in mRCC, retrospective evidence exists suggesting that schedule 2/1 may be at least as efficacious with an improved safety profile. However, no prospective data exists comparing the two schedules in terms of tolerability. Studies are needed to quantitate the functional cardiovascular and muscular changes induced by these two regimens. Specifically, the phenomenology of fatigue in this setting needs to be better understood. Our overall hypothesis is that schedule 2/1 of sunitinib is not only better tolerated but will be associated with less fatigue and functional cardiovascular/muscular toxicity than the 4/2 schedule. In this study, the first in a continuum of research, we will obtain data on the magnitude of VO2peak decline (mean, median, standard deviation, etc.) in each arm in order to design a more definitive study to test this hypothesis. Because future studies will include exercise training as a component, data on physiological determinants of VO2peak will be useful to design an optimal exercise training program.

## **4 OBJECTIVES AND ENDPOINTS**

All endpoints will be evaluated at the time points specified in the Schedule of Events at the beginning of **Section 8**. See **Section 11** for Statistical Methods and Data Analysis. Key comparisons will be the change from Day 1 (week 1) to Day 85 (through week 12).

	Objective	Endpoint	Analysis
Primary	To estimate the change in VO 2 peak after 12 weeks from baseline in treatment-naïve mRCC patients treated with sunitinib on schedule 4/2 and 2/1	Change in VO 2 peak with sunitinib on schedule 4/2 or 2/1 after 12 weeks from baseline	See Section 11.1 to Section 11.4
Key Secondary	To assess the effects on the primary physiological determinants of VO 2 peak (e.g., resting and stress cardiac function and muscle function, defined as cross-sectional area,	
 
Rest and Exercise Left Ventricular Ejection Fraction (LVEF) and Cardiac Function by 2-D and 3-D echocardiography (2DE/3DE) including Global Longitudinal Strain (GLS)
 
	See Section 11.5

	Objective	Endpoint	Analysis
	strength endurance and maximal strength)	
 
Upper and lower extremity maximal muscular strength: 
 
voluntary one-repetition maximum (1-RM)
 
muscular endurance (number of repetitions to fatigue at 70% of 1-RM)
 
 
 
Muscle cross-sectional area (CSA) of the major muscles near L3 (CT scans and Slice-O-Matic® software)
 
	
Other Secondary	To evaluate changes in other measures of physical functioning/functional capacity and correlate with changes in VO 2 peak	Objective assessments (i.e., chair-stand test, timed up and go, 6-minute walk distance) of functional capacity	See Section 11.5
Other Secondary	To estimate the effects on patient-reported outcomes (i.e., fatigue and QOL)	Functional Assessment of Chronic Illness Therapy (FACIT)-Fatigue and Functional Assessment of Cancer Therapy-Kidney Symptom Index-19 (FKSI-19)- Godin Leisure Time Exercise Questionnaire	See Section 11.5
Other Secondary	To evaluate co-existent depression	Hospital Anxiety and Depression Scale (HADS)	See Section 11.5
Exploratory	To evaluate safety and tolerability of both: (a) Sunitinib and (b) Exercise testing	Eligibility rate, attrition rate, and adverse event rate (CTCAE v4.0) in each arm	See Section 11.5
Exploratory	To determine the dose intensity of sunitinib	Patient- reported drug diaries	See Section 11.5
Exploratory	To estimate early change in VO 2 peak at 4-5 weeks compared with baseline	Change in VO 2 peak from baseline to 4-5 weeks	See Section 11.5
Exploratory	To collect plasma angiome samples for analysis and correlation with primary and key secondary endpoints	Plasma angiome multiplex ELISA	See Section 11.5
Exploratory	To use real-time electronic monitoring to describe the following over the study period (subset of patients): 
 
(a) Changes in daily physical activity
 
(b) Changes in daily blood pressure
 
	
 
(a) Steps per day
 
(b) Daily blood pressure (mmHg) reading
 
	See Section 11.5

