## 5 INVESTIGATIONAL PLAN

### 5.1 Study Design

Proposed is a randomized (1:1) prospective trial to determine changes in VO2peak in patients with treatment-naïve mRCC treated with sunitinib therapy on two different common schedules (see **Section 2**). Patients randomized to sunitinib schedule 4/2 (**Arm A**) will receive sunitinib at 50 mg daily for 4 weeks on, followed by 2 weeks off, per standard of care. Patients randomized to sunitinib schedule 2/1 (**Arm B**) will receive sunitinib 50 mg daily for 2 weeks on, followed by 1 week off. All subjects will undergo detailed functional capacity assessments at baseline, 4-5 weeks, and after 12 weeks.

Specific recommendations for management of possible AEs, along with guidelines for dose delay/modification or discontinuation from study treatment are provided in this section, based on best evidence from contemporary trials and retrospective studies.

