## PATIENT REPORTED OUTCOMES END POINTS (FACIT-F, FKSI-19, Godin Leisure Time Exercise Questionnaire)

Sunitinib treatment causes fatigue and worse QOL; however, the changes that occur with sunitinib on schedule 2/1 and 4/2 have not been prospectively described. Therefore, we propose to describe the changes that occur in this setting.

Because fatigue is a patient reported outcome (PRO) of interest, we will evaluate it using the Functional Assessment of Chronic Illness Therapy – Fatigue (FACIT-F) questionnaire. The FACIT-F measures severity and impact of fatigue on functioning and health-related quality of life (HRQL) experienced in past seven days [Cella, 2002]. It has been used previously to evaluate fatigue with anti-angiogenesis treatments, including assessments for sunitinib [Motzer, 2005; Beaumont, 2006; Motzer, 2013]. The Functional Assessment of Cancer Therapy-Kidney Symptom Index -19 (FKSI-19) is a disease-specific measure that measures disease and

treatment-related symptoms specifically in renal cancer patients [Rosenbloom, 2007; Rosenbloom, 2008; Rao, 2008]. It includes patient self-reports on experience of symptoms in the past seven days such as lack of energy, pain, bone pain, shortness of breath, fatigue, blood in urine, etc. Fksi-19 has been used in a contemporary trial of sunitinib in mRCC. Finally, because it will be important for interpretation of our data to understand activity levels in both arms, we will evaluate leisure time exercise habits with the simple Godin Leisure Time Exercise Questionnaire.

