## 11.5 Secondary and Exploratory Objectives

For subjects with VO2 peak measures at week 4 or week 5, descriptive statistics including mean, standard deviation, minimum and maximum of VO2peak changes from baseline to week 4 and to week 5 will also be reported to assess early effects of each sunitinib schedule. Descriptive statistics for other secondary and exploratory endpoints will also be reported for each sunitinib schedule.

In addition, a random effects model will be used to assess the effect of different sunitinib schedules on the VO2 peak change. In the model repeated measurements of VO2 peak change at week 4, 5 and through week 12 from baseline are outcomes, schedule indicator (0 for schedule 4/2, 1 for schedule 2/1) is chosen as the main factor, baseline VO2 peak value and patient characteristics are other included covariates. Similarly, random effects models with other continuous repeated measures (i.e., resting and stress cardiac function and muscle strength) as dependent variables will also be used to analyze the schedule effects.

Sensitivity analyses will be performed for the primary endpoint and key secondary endpoint using Last Value Carried Forward (LOCF) methods. The intent of this sensitivity analysis is to assay the robustness of results observed in the modified ITT population.

Eligibility rate, acceptance rate and adverse event rate will be reported descriptively.

Eligibility rate is defined as the number of subjects eligible for the study divided by the number approached for the study (i.e., screen fail rate).

Acceptance rate is defined as the number of patients agreeing to participate divided by total number randomized.

Rates of adverse events, classified by CTCAE v4.0, will be displayed by body system and preferred term for each arm.

For analysis of the plasma angiome multiplex ELISA data, correlations among analytes will be evaluated by Spearman analysis. Analyte levels at baseline and changes on-treatment will be correlated with baseline VO2peak and changes in VO2peak, respectively.

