## APPENDIX E HADS

**Instructions:** Doctors are aware that emotions play an important part in most illnesses. If your doctor knows about these feelings he or she will be able to help you more. This questionnaire is designed to help your doctor know how you feel. Read each item and circle the reply which comes closest to how you have been feeling in the past week. Don't take too long over your replies: your immediate reaction to each item will probably be more accurate than a long thought out response.

D	A		D	A	
		I feel tense or 'wound up':			I feel as if I am slowed down:
3		Most of the time	3		Nearly all the time
2		A lot of the time	2		Very often
1		From time to time, occasionally	1		Sometimes
0		Not at all	0		Not at all
		I still enjoy the things I used to enjoy:			I get a sort of frightened feeling like 'butterflies' in the stomach:
0		Definitely as much	0		Not at all
1		Not quite so much	1		Occasionally
2		Only a little	2		Quite Often
3		Hardly at all	3		Very Often
		I get a sort of frightened feeling as if something awful is about to happen:			I have lost interest in my appearance:
3		Very definitely and quite badly	3		Definitely
2		Yes, but not too badly	2		I don't take as much care as I should
1		A little, but it doesn't worry me	1		I may not take quite as much care
0		Not at all	0		I take just as much care as ever
		I can laugh and see the funny side of things:			I feel restless as I have to be on the move:
0		As much as I always could	3		Very much indeed
1		Not quite so much now	2		Quite a lot
2		Definitely not so much now	1		Not very much
3		Not at all	0		Not at all
		Worrying thoughts go through my mind:			I look forward with enjoyment to things:
3		A great deal of the time	0		As much as I ever did
2		A lot of the time	1		Rather less than I used to
1		From time to time, but not too often	2		Definitely less than I used to
0		Only occasionally	3		Hardly at all
		I feel cheerful:			I get sudden feelings of panic:
3		Not at all	3		Very often indeed
2		Not often	2		Quite often
1		Sometimes	1		Not very often
0		Most of the time	0		Not at all
		I can sit at ease and feel relaxed:			I can enjoy a good book or radio or TV program:
0		Definitely	0		Often
1		Usually	1		Sometimes
2		Not Often	2		Not often
3		Not at all	3		Very seldom

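### The Day 85 key comparison reads fatigue and quality of life over a planned drug-free week, after unequal breaks in the two arms, while the on-drug reading at Day 29/36 has no key role

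*Combined protocol and SAP*

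**What the plan says.** **Objective and time point.** Section 4 lists "To estimate the effects on patient-reported outcomes (i.e., fatigue and QOL") as an other-secondary objective, measured by FACIT-Fatigue, FKSI-19 and the Godin questionnaire. HADS serves a separate other-secondary objective on depression. The text above the objectives table refers all endpoints to the Schedule of Events and adds "Key comparisons will be the change from Day 1 (week 1) to Day 85 (through week 12"). No endpoint is excepted. An early-change objective is named for VO2peak only.

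**Recall period.** Section 5.5 states: "The FACIT-F measures severity and impact of fatigue on functioning and health-related quality of life (HRQL) experienced in past seven days". The printed FACIT-F and FKSI-19 forms (Appendices B and C) use the same 7 days. HADS (Appendix E) asks the patient to "circle the reply which comes closest to how you have been feeling in the past week". The Godin form asks about a typical week, so the count below does not apply to it.

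**Dosing.** Under Section 5.1, Arm A "will receive sunitinib at 50 mg daily for 4 weeks on, followed by 2 weeks off, per standard of care". Arm B takes the same daily dose "for 2 weeks on, followed by 1 week off". Table 3, footnote d, makes Day 1 the day of the first dose. Section 5.1.1 allows dose reductions but keeps the schedule fixed.

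**Visits.** Table 3 collects the three forms at baseline, at Day 29 (4/2) or Day 36 (2/1), and at Day 85. Both on-study visits have a ±3-day window.

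**Analysis.** Section 11.5 plans descriptive statistics by schedule for the secondary endpoints. It also plans a random effects model of the schedule effect for VO2peak change and for other continuous repeated measures, which it spells out as "resting and stress cardiac function and muscle strength".

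**The concern.** Section 3.3 hypothesises that "schedule 2/1 of sunitinib is not only better tolerated but will be associated with less fatigue", and Section 5.5 sets out to describe how fatigue and quality of life change on each schedule. A 7-day recall form can only speak to the week before the visit. If that week falls in a planned break, the comparison the plan calls key does not describe fatigue while the patient is taking sunitinib.

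Two things are at stake. Within each arm, the change from baseline may look smaller than it is on drug. Between arms, the contrast may partly reflect how long each arm has been off drug at the visit. The plan needs to say which state of the patient its key fatigue comparison is meant to capture.

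**Working it through.** **1. Calendar, checked against the plan's own figure.** Counting from Day 1 as first dose:

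- Arm A (4/2) is on drug on day d if (d − 1) mod 42 < 28.
- Arm B (2/1) is on drug on day d if (d − 1) mod 21 < 14.

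Over 42 days, Arm A has 28 dosing days and Arm B has 2 × 14 = 28. At 50 mg this is 28 × 50 = 1400 mg in each arm, as Section 5.4 states. The calendar is:

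- 4/2: on 1–28, off 29–42, on 43–70, off 71–84, on from 85.
- 2/1: on 1–14, off 15–21, on 22–35, off 36–42, on 43–56, off 57–63, on 64–77, off 78–84, on from 85.

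**2. Recall at Day 85.** A visit on day v recalls days v − 7 to v − 1. For v = 85 that is Days 78–84. Planned dosing days inside the recall, across the window:

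| Visit day | 82 | 83 | 84 | 85 | 86 | 87 | 88 |
|---|---|---|---|---|---|---|---|
| 4/2 | 0 | 0 | 0 | 0 | 1 | 2 | 3 |
| 2/1 | 3 | 2 | 1 | 0 | 1 | 2 | 3 |

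At nominal Day 85 the count is 0 of 7 in both arms. A visit up to three days early brings dosing days into the recall on 2/1 only; a late visit adds them equally. If the visit day itself is counted and a dose has already been taken, the Day 85 count is 1 of 7 in both arms.

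**3. Time off drug before Day 85.** The last planned dose is Day 70 on 4/2 and Day 77 on 2/1. The drug-free days are 84 − 70 = 14 and 84 − 77 = 7.

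**4. Recall at the early visit.** Day 29 on 4/2 recalls Days 22–28; Day 36 on 2/1 recalls Days 29–35. Both are 7 of 7 dosing days. In both arms a visit up to three days early also gives 7, and a visit one, two or three days late gives 6, 5 or 4.

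**5. What a pooled model would do.** As described, the Section 11.5 model has a schedule indicator, the baseline value and patient characteristics. It names no visit term and no schedule-by-visit term. Applied to FACIT-F, it would merge a reading with 7 of 7 dosing days and one with 0 of 7 into a single schedule effect.

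**6. Precision of an early comparison.** With about 15 patients per arm (Section 11.6), the 95% half-width for a difference in mean change is about 2.05 × √(2/15) = 2.05 × 0.365 = 0.75 standard deviations of the change, before any gain from baseline adjustment.

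**The case against.** **On-drug fatigue is not lost.** The forms are collected at Day 29/36, and Section 11.5 does not confine its descriptive statistics to Day 85. Fatigue is also an adverse event of special interest (Section 9.1.1), and adverse event rates are reported by arm. This stands. The fault lies in which comparison is called key, not in missing data.

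**Little formally depends on the label.** FACIT-F is an other-secondary endpoint with no alpha or decision rule, and Section 3.3 leaves the test of the hypothesis to a later study. This also stands and limits the weight of the point. It does not make Day 85 a description of fatigue on drug.

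**Stronger readings are tempting but unsupported.**

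- A reader might infer that Day 85 catches fatigue at its lowest point, in recovered patients. No section gives the course of fatigue within a cycle, and Section 5.2.1 names hypothyroidism as a possible contributor. The most the documents offer is Table 1, which expects severe fatigue to ease on interruption. That supports likely understatement, not its size.
- A reader might infer a bias toward no difference between arms. That does not follow. If breaks relieve fatigue, 14 days off against 7 could favour 4/2.
- A reader might infer that FACIT-F gets no between-schedule estimate. The list in Section 11.5 follows an *i.e.*, which this protocol often uses to introduce examples. FACIT-F, with two post-baseline values, fits a repeated-measures model better than exercise echocardiography, which has one. The wording is ambiguous.

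**Day 29/36 has its own slant.** It is early, and it sets the end of a 28-day block against the end of a 14-day block, arguably the least favourable moment for 4/2. This is a good reason to keep Day 85 and add the early comparison beside it.

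**The performance tests at Day 85 fall in the same phase.** That is true. This point is confined to the questionnaires, whose stated recall lets the dosing days be counted exactly.

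**Conclusion.** The point holds as a matter of timing and labelling. At nominal Day 85 the recall of FACIT-F, FKSI-19 and HADS contains no planned dosing day in either arm, and the arms differ twofold in time off drug. The comparison named as key therefore describes the end of a scheduled break, and its between-schedule contrast is confounded with time since last dose. Understatement of on-drug fatigue is likely; its amount, and the net direction of any between-arm distortion, cannot be determined from the documents.

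The counts assume dosing on plan. Interruptions or delays would shift the cycle for individual patients. They also assume that Section 4's sentence covers the questionnaires, which is its plain reading since it excepts none. The primary endpoint, type I error and power are unaffected. The change is worth making because the better-matched reading is already being collected.

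**What to change.** - In Sections 4 and 11.5, add baseline to Day 29 (4/2) / Day 36 (2/1) as a pre-specified key on-drug comparison for FACIT-F, FKSI-19 and HADS.
- Keep the Day 85 comparison for these instruments, label it *end of scheduled break*, and state the unequal time off drug wherever the arms are compared.
- In Section 11.5, specify the between-schedule difference in FACIT-F at Day 29/36, adjusted for baseline FACIT-F, with a 95% CI.
- State that the two visits will not be pooled into one schedule effect for these outcomes, and make clear whether the listed measures in the random effects paragraph are examples or the full set.

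The cost is protocol and SAP wording plus one small analysis, with no new visits, forms or patients. The limits should be stated with the result. The early visit shows early rather than cumulative fatigue and falls 7 days later in Arm B. It compares blocks of different length, and the interval will be wide, so the estimate serves planning rather than proof.
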